### **9. DATA ANALYSIS AND STATISTICAL CONSIDERATIONS**

#### **9.1. Hypotheses and Treatment Comparisons**

The primary focus of the statistical analysis is to describe safety and characterize the preliminary pharmacokinetics of GSK2646264 through estimates of parameters and their variability. Thus, an estimation approach will be taken to provide a plausible range of values, where appropriate, with no formal hypothesis testing.

##### **9.1.1. Precision Estimation**

This study is designed to estimate the effect of GSK2646264 relative to Placebo on comparison of interest. No formal hypothesis will be tested. Point estimates and corresponding 95% confidence intervals will be constructed.

## 9.2. Sample Size Considerations & Statistical Analyses

There are no formal hypotheses to be tested. An estimation approach will be taken and 95% confidence intervals will be constructed to provide a range of plausible values for the comparisons of interest.

Approximately 42 subjects will be randomised in total, consisting of 18 subjects in Part A (9 subjects on first dose group and 9 subjects in second dose group), 12 subjects in Part B and 16 subjects in Part C of the study. The sample size is based on feasibility and not driven by any formal hypothesis testing.

### 9.2.1. Sample Size Sensitivity

For Part A, based on a sample size of 9 randomised subjects, it is estimated that the 95% confidence interval for the percent of inhibition effect will be within 18.5% of the estimate for the weal size assuming standard deviation of 24, within 8.5% of the estimate for the flare size assuming standard deviation of 11 and within 17.7% of the estimate for the weal volume assuming standard deviation of 23 ([Schoepke, 2011](#)).

**Table 10 Results of the sensitivity analyses for part A**

N	Percent of Inhibition Weal Size		Percent of Inhibition Flare Size		Percent of Inhibition Weal Volume	
	Precision around estimate	SD	Precision around estimate	SD	Precision around estimate	SD
9	15.4	20	6.9	9	15.4	20
9	16.9	22	7.7	10	16.1	21
9	18.5	24	8.5	11	17.7	23
9	20.0	26	10	13	19.2	25
9	21.5	28	11.5	15	20.8	27

### 9.2.2. Sample Size Re-estimation

No sample size re-estimation will be performed.

No sample size re-estimation is currently planned for this study. However, if during the course of the study, new information becomes available about clinically meaningful differences or variability estimates, a blinded sample size re-estimation may be conducted. Full details of the procedure used would be specified in the RAP, and any subsequent change to the target sample size would be documented in a protocol amendment.

### **9.3. Data Analysis Considerations**

#### **9.3.1. Interim Analysis**

No formal interim analyses are planned.

##### **9.3.1.1. Summary of safety reporting from Part A**

A summary of the safety data from Part A will be performed once all subjects are recruited and completed all visits. This summary will include PK and PD data from Part A of study cohort. All safety data including adverse events, laboratory tests, ECGs and vital signs will be reviewed. The decision to proceed to higher dose strengths will be made by the investigator and the GSK SMC review team based on assessment of safety and pharmacokinetic data of the studied doses.

##### **9.3.1.2. Summary of exposure and safety reporting from Part B: first 4 subjects**

The safety, tolerability, and preliminary exposure data from Part B (first 4 subjects) will be reviewed by the SMC once those subjects have completed the study up to and including the follow-up visit. The decision for the dosing regimen and study population for the remainder of Part B, and Part C will be made by the SMC review based on assessment of safety, and pharmacokinetic data of the studied doses.

This study is double blind (sponsor open), where the subject, investigator and site staff will remain blinded to the treatment allocation.

##### **9.3.1.3. Summary of exposure and safety reporting from Part C: first 4 subjects**

Preliminary safety and tolerability, and potentially biomarkers of interest), and preliminary exposure data from Part C (first 4 subjects) may be reviewed by the sponsor once those subjects have completed the study up to and including the follow-up visit. The decision for the potential adjustment of the dosing regimen and/or study population for the rest of Part C will be made by the sponsor review based on assessment of safety and pharmacokinetic data of the studied doses. If required, a discussion with the SMC regarding any changes or adjustments to the dosing regimen in Part C will be held.

Other experts from CPMS and DMPK, at GSK, may be consulted to review blinded placebo/active data (safety, PK and any available PD) during the study for further relevant input. In-stream review of the data may also take place at any time at SRT (Safety Review Team) meetings.

#### **9.3.2. Final Analyses**

##### **9.3.2.1. Safety Analyses**

Safety data will be presented in tabular and/or graphical format and summarized descriptively according to GSK's standards.

No formal statistical analysis of the safety data will be conducted. The following safety assessments will be listed and summarized where appropriate: extent of systemic

exposure, local skin reactions, adverse events, clinical laboratory evaluations, concurrent medications, vital signs, ECG interval data, and other relevant safety assessments. Adverse events, local skin reaction assessments, and liver chemistry will be summarized by doses strength (where possible) and BSA.

### **9.3.2.2. Pharmacokinetic Analyses**

Pharmacokinetic analysis will be the responsibility of the Clinical Pharmacokinetics Modelling and Simulation Department, CPMS, GlaxoSmithKline and Parexel. Plasma concentration-time data will be recorded in tabular and/or graphical form. From GSK2646264 concentration-time data, the following pharmacokinetic parameters will be determined using the currently approved and validated software, as data permit: maximum plasma concentration ( $C_{max}$ ); time of maximum plasma concentration ( $T_{max}$ ); area under the plasma concentration-time curve (AUC) and apparent terminal elimination half-life ( $t_{1/2}$ ), if data permit.

Pharmacokinetic data will be presented in graphical and/or tabular form and descriptively summarized. Pharmacokinetic data will be stored in the Archive, GlaxoSmithKline.

### **9.3.2.3. Pharmacodynamic/Biomarker Analyses**

#### **9.3.2.3.1. Part A & B: Healthy and Cold urticaria Subjects**

Raw data and percent of inhibition for each PD parameter (i.e. longest weal diameter, perpendicular weal length, weal area, weal volume, and flare erythema assessments) will be provided by strength, BSA, and day. Descriptive summary statistics (i.e. n, minimum, arithmetic mean, standard error, median, maximum) for both raw and percent of inhibition for Part B will be calculated by dose strength, BSA, and day. Additionally, figures will be produced for PD parameters. No formal statistical testing of the PD data will be conducted.

Descriptive summary statistics for percent of inhibition of systemic CD69 biomarker will be provided by strength, BSA and day.

#### **9.3.2.3.2. Part C: Chronic Spontaneous Urticaria Subjects**

UAS7

PD assessment in CsU subjects will be measured using a composite score UAS7.

The UAS7 score will be calculated using the 7 consecutive days sum. A score will be derived for the screening visits and for the post dose visits. In the presence of one or more missing daily UAS7 scores, the following algorithm will be applied:

- If a patient has at least 4 non-missing daily UAS7 scores within the 7 days, the UAS7 score will be calculated as the sum of the available eDiary UAS7 scores in that week, divided by the number of days that have a non-missing diary UAS7 score, multiplied by 7.

- If there are less than 4 non-missing daily UAS7 scores, then the UAS7 score will be missing.

Change from baseline in UAS7 will be derived as post dose UAS7 total score minus the Baseline UAS7 total score (screening). The mean and standard deviation of the change from baseline in UAS7 for each treatment group will be presented. The change from baseline in UAS7 will be analysed using the ANCOVA model including treatment, baseline UAS7 and location of treatment. Estimates of the means and treatment difference and associated 95% confidence intervals will be presented. Analysis of each component will be performed similar to UAS7 analysis.

Summary statistics for each component of UAS7 questionnaire will be provided by visit.

For CsU Subjects (Part C), descriptive summary statistics for percent of inhibition of CD69 biomarker will be provided by strength, BSA and day if samples are taken in Part C.

More details will be provided in the RAP.

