**Figure 3 Schematic showing Part B Dosing in Cold urticaria patients**

**3.1.5. Part C : A double-blind (sponsor unblinded) placebo-controlled, randomised to active or placebo treatment repeat dose study (3 doses over 7 days), in subjects with mild to moderate Chronic Spontaneous Urticaria (CsU)**

Subjects will be randomised to a 3:1 ratio to receive active treatment or placebo applied to areas of the body chosen by the investigator once a day every 3 days, over a total period of 7 days. Dosing will occur on days 1, 4 and 7. The chosen area where cream is applied will remain the same throughout the dosing period. Dosing in Part C will only commence once relevant data from the first four subjects in Part B have been reviewed, to allow greater confidence in predictions of the pharmacokinetics in Part C. The BSA over which study treatment will be administered in Part C will be 10%, but is subject to change, if appropriate, based on preliminary data from the first 4 subjects in Part C. However, the maximum BSA will not exceed 20% (see [Figure 4](#) for a visual representation of the dosing schedule).

[figure not shown]
The first 4 subjects of Part C will be randomised so that one of the 4 subjects will receive placebo and the three other subjects will receive GSK2646264. An informal review of the preliminary data from the first 4 subjects may be conducted after they have completed the study. PK, safety, and tolerability, up to and including the follow-up visit, will be reviewed by the Sponsor (See [Section 5.5](#)). If required, a discussion with the SMC regarding any changes or adjustments to the dosing regimen in Part C will be held. Recruitment of the full planned cohort (n=16) may continue during any data review.

The timing and the assessments to be completed at each visit are provided in the Time and Event tables ([Section 6.1.4](#)). Early termination of this patient group may occur due to feasibility of recruitment and stopping criteria see ([Section 5.5](#) and [Section 5.6](#)). Following inclusion in the study, subjects will be randomised. 10 mg/cm^2 of 1%

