GSK2646264 cream or placebo cream will be applied to a given BSA once per day, every 3 days, on days 1, 4 and 7, on areas of the body chosen by the investigator. The areas where cream is applied will remain the same for each day of dosing. The 10 % BSA can be distributed between the arms, legs and torso for an individual subject and will be decided by the investigator prior to randomisation. This pattern of cream application will remain the same for the duration of dosing. The maximum % BSA and the frequency of dosing will be decided after Part A and n=4 in Part B of the study but will not exceed 20% BSA.

The subjects will be dosed in the unit for the first dose on day 1 and then discharged from the clinic. Subjects will return to the clinic prior to the dose and specified assessments on days 4 and 7. Subjects will be asked to complete a daily diary over the 7 days. Details of the diary will be provided in the Study Procedures Manual (SPM)

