## 5.4. Treatment Assignment

Subjects will be assigned to treatment in accordance with the randomization schedule generated by Parexel, prior to the start of the study. Randomisation will occur within each cohort of study. Subjects will be randomised to 1:1 to receive bilateral treatment of GSK2646264 or placebo in Part A. For Parts B & C, subjects will be randomised 3:1 active:placebo respectively, to receive either GSK2646264 or placebo.

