### ***The Angioedema Activity Score***

Each AAS item will be scored between 0 to 3 and daily total score AAS score will range between 0 and 15. The daily AAS score will summed to compute a 7-day total scores for screening (baseline) and post dose. Change from baseline, the 7 day total and individual item scores will be calculated. The mean and standard deviation of the change from baseline in total and individual item score for each treatment group will be presented.. The change from baseline will be analysed using the ANCOVA model including treatment, baseline and location of treatment as covariates. Point estimates and 95% confidence intervals will be presented. Missing values will not be imputed. More details will be provided in RAP.

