
 • Change from baseline in composite total UAS7 score and components
Model Specification

 • Endpoint will be analysed using paired t test and ANCOVA to compare the treatment groups. • ANCOVA model will be fitted as: Post-Pre dose as response and pre dose as covariate.
Model Checking

 • Refer to Appendix 8: Model Checking and Diagnostics for Statistical Analyses.
Model Results Presentation

 • Estimated treatment difference and 95% confidence intervals will be presented.
Analysis of UAS7 Components

 • Analysis of UAS7 components will be performed similar to total UAS7 composite score • Summary Statistics for each component of UAS7 questionnaire will be provided by visit.
Note:

 • Composite score UAS7 will be derived using key urticaria symptoms (number of weal, Itch/Pruritus). The UAS7 score will be calculated using the summation of the 7 consecutive days sum. • Other questions collected as part of UAS7 questionnaire will be listed.

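### The protocol's three Part C ANCOVAs adjust for a treatment location that has no defined coding, and the SAP fits no such term

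*Protocol*

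**What the plan says.** **Protocol, models.** For UAS7, section 9.3.2.3.2 states that "The change from baseline in UAS7 will be analysed using the ANCOVA model including treatment, baseline UAS7 and location of treatment". The AAS text that follows and the DLQI text in 9.3.2.4.1 call for change from baseline to be analysed "using the ANCOVA model including treatment, baseline and location of treatment as covariates". None of the three says what values location takes. UAS7 and AAS refer to the RAP for further detail.

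**Protocol, application and allocation.** Section 3.1.5 says: "The 10 % BSA can be distributed between the arms, legs and torso for an individual subject". The investigator decides this before randomisation and it then stays fixed. Section 5.4 says "Randomisation will occur within each cohort of study" and "For Parts B & C, subjects will be randomised 3:1 active:placebo respectively, to receive either GSK2646264 or placebo". No stratum for treated site is named.

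**SAP.** For UAS7 (9.1.2.1) and AAS (9.1.2.2) the specification is "ANCOVA model will be fitted as: Post-Pre dose as response and pre dose as covariate", with a paired t test named beside it. DLQI (9.1.3.1) has a paired t test only, and the programming note for Table 5.14 says no treatment comparison is involved. Section 5 plans no examination of covariates, and Appendix 7 is marked not applicable. Section 2.1, which lists departures from the protocol analysis, does not mention location.

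**The concern.** There are two linked defects.

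First, the covariate is not defined. A patient can be treated on one, two or three regions, so there are 2³ − 1 = 7 possible site sets. An analyst following the protocol must decide whether location means the main site, three yes/no indicators, seven combinations or a share of treated area. Nothing on file makes that choice.

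Second, the document meant to supply the detail contradicts the protocol: an analyst following the SAP fits no location term and has no between-arm model for DLQI.

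What is at stake is the estimated treatment difference and its 95% interval for three exploratory endpoints, in a comparison with only four placebo subjects. The width of that interval would depend on an unrecorded choice. The sponsor's review team is unblinded (5.5, 5.9) and may look at the first four Part C subjects (9.3.1.3), so the choice could be made with the data in view.

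**Working it through.** **Inputs.** Section 9.2 gives "12 subjects in Part B and 16 subjects in Part C of the study", and 3.1.5 and 4.1 also give 16 for Part C. At 3:1 this is 16 × 3/4 = 12 active and 16/4 = 4 placebo. Section 3.1.5 adds: "The first 4 subjects of Part C will be randomised so that one of the 4 subjects will receive placebo". Blocks of four for all 16 subjects is an assumption. The documents give no UAS7 standard deviation and no site frequencies, so results are in residual-SD units over assumed frequencies.

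**The plan's own precision figure.** None exists for Part C. Section 9.2.1 gives 18.5 for weal size in Part A (N = 9, SD 24). t(0.975, 8) × 24/√9 = 2.306 × 8 = 18.45, which agrees. All 15 entries of Table 10 reproduce this way, so t-based half-widths match the plan's method.

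**Formula for Part C.** With q covariate columns (baseline plus location), the approximate half-width in residual SDs is

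t(0.975, 14 − q) × √(1/12 + 1/4) × √(13/(13 − q)).

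The middle term is 0.577. The last is the expected variance inflation from chance imbalance in random covariates. Break-even is the share of residual variance that location must explain to restore the original width: 1 − 1/ratio².

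| Coding | q | Residual df | Half-width | Ratio | Break-even |
|---|---|---|---|---|---|
| No location | 1 | 13 | 2.160 × 0.577 × 1.041 = 1.30 | 1 | – |
| 3 exclusive levels | 3 | 11 | 2.201 × 0.577 × 1.140 = 1.45 | 1.116 | 20% |
| 3 yes/no indicators | 4 | 10 | 2.228 × 0.577 × 1.202 = 1.55 | 1.191 | 29% |
| 7 combinations, all present | 7 | 7 | 2.365 × 0.577 × 1.472 = 2.01 | 1.548 | 58% |

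**Simulation of the design matrix.** There were 8,000 runs per scenario, with 12 v 4 in blocks of four, baseline included, and location unrelated to treatment and outcome. Each pair is the result for equal or balanced frequencies, then for uneven ones.

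| Coding | Median widening | Mean | 90th percentile |
|---|---|---|---|
| 3 exclusive levels | 8.2%, 7.5% | 11.3%, 10.8% | 23%, 21% |
| 3 yes/no indicators | 14.4%, 14.0% | 18.3%, 18.3% | 36%, 35% |
| 7 combinations | 35.4%, 30.5% | 42.7%, 37.0% | 74%, 66% |

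The uneven frequencies were 0.60/0.25/0.15 for three levels, 0.7/0.5/0.4 for the indicators, and 0.30 down to 0.05 for seven levels. The medians are below the formula values because the widening is right-skewed and, with seven levels, not all occur in every trial.

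**Source of the loss.** The lost degrees of freedom alone widen the interval by 2%, 3% and 9.5%. The rest is imbalance between arms. With k equally likely levels, the chance that an active subject's level holds none of the four placebo subjects is ((k − 1)/k)⁴, which is 20% for k = 3 and 54% for k = 7. Such subjects add little or nothing to the treatment contrast. The contrast itself was not estimable in under 0.3% of runs.

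**The case against.** Location is fixed before randomisation, so it is a legitimate baseline covariate and adjusting for it does not bias the comparison. Every widening above assumes that it explains nothing. That may be wrong for UAS7: protocol 2.3.3 and SAP 2.2 restrict that objective to the treated skin, although the diary items in protocol Appendix 3 name no body area. A moderately prognostic location with a compact coding could pay for itself. This stands, and it rules out saying that location has nothing to explain.

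A reader might infer that the adjustment costs much of the precision of Part C. The documents do not support that in general. It holds only if every site combination becomes its own level, and no document says so; with three levels or three indicators the median loss is about 8% or 14%.

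A reader might also take the affected interval to be the main output of Part C. It is not: safety and tolerability are primary, pharmacokinetics secondary, these scores exploratory, and nothing is formally tested.

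It can also be said that the SAP already drops location, so nothing needs doing. But that SAP states that it is based on protocol amendment 2, with a bilateral design and 12 patients in Part C. Nor does its age explain the omission for UAS7: protocol Appendix 8, under amendment 3, shows location already in the UAS7 model that was being replaced. The SAP therefore does not settle which model applies.

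**Conclusion.** The point holds as an undefined covariate together with an unreconciled protocol–SAP conflict. Following the protocol means inventing a coding; following the SAP means fitting no location term and having no between-arm DLQI analysis. If location explains none of the outcome, the median cost in interval width is about 8%, 14% or 30–35% depending on the coding. It shrinks to nothing, or becomes a gain, once location explains more than about 20%, 29% or 58% of residual variance. These sizes rest on 12 v 4 subjects, assumed site frequencies and assumed blocks of four. The conflict and the missing definition rest on the text alone. Because the endpoints are exploratory and estimation-only, this should be fixed but does not threaten the trial's primary objective.

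**What to change.** Make treatment plus baseline the model for UAS7, AAS and DLQI in protocol 9.3.2.3.2 and 9.3.2.4.1 and in SAP 9.1.2.1, 9.1.2.2 and 9.1.3.1. This replaces the DLQI paired t test and means correcting the note to Table 5.14. Record the removal of location in SAP 2.1, and list treated sites by subject.

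If the sponsor wants location kept, state its coding (for example, the share of treated area per region) before any unblinded review of Part C, and use it only in a sensitivity analysis.

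The cost is wording plus one listing. The downside is that the main model makes no adjustment for a possible site effect, which could matter for UAS7 if it is scored within the treated area only; the sensitivity analysis would address that.

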### ***The Angioedema Activity Score***

Each AAS item will be scored between 0 to 3 and daily total score AAS score will range between 0 and 15. The daily AAS score will summed to compute a 7-day total scores for screening (baseline) and post dose. Change from baseline, the 7 day total and individual item scores will be calculated. The mean and standard deviation of the change from baseline in total and individual item score for each treatment group will be presented.. The change from baseline will be analysed using the ANCOVA model including treatment, baseline and location of treatment as covariates. Point estimates and 95% confidence intervals will be presented. Missing values will not be imputed. More details will be provided in RAP.

#### **9.3.2.4. Health Outcomes Analyses**

**For CsU subjects, quality of life will be measured using the Dermatology Life Quality Index (DLQI) questionnaire.**

##### **9.3.2.4.1. Dermatology Life Quality Index**

A total score and its six individual domains (symptoms and feelings, daily activities, leisure, work and school, personal relationships, and treatment) will be calculated. Change in DLQI score from baseline in total and individual domain scores will be calculated. The mean and standard deviation of the change from baseline in total and individual domain score will be presented. The change from baseline will be analysed using the ANCOVA model including treatment, baseline and location of treatment as covariates. Point Estimates and 95% confidence intervals will be presented. More details on scoring method will be provided in RAP.

